3.1.2. Laboratory Data

Safety laboratory tests will be performed as described in the protocol.

The investigator must review the laboratory report, document this review, and record any clinically significant changes occurring during the study in the AE section of the CRF. Clinically significant abnormal laboratory test findings are those that are not associated with the underlying disease, unless judged by the investigator to be more severe than expected for the participant's condition.

Baseline will be the last pre-dose measurement in each study period.

To determine if there are any clinically significant laboratory abnormalities, the hematological, clinical chemistry (serum) and urinalysis safety tests will be assessed against the criteria specified in the sponsor reporting standards. The assessment will take into account whether each participant's baseline test result is within or outside the laboratory reference range for the particular laboratory parameter.

3.1.3. Vital Signs

Single supine blood pressure and pulse rate measurements will be taken at screening, follow-up visit and at early termination (if applicable). Triplicate supine measurements will be taken at all other times as detailed in the Schedule of Activities (SoA) in the protocol. The average of the triplicate measurements will be calculated prior to analyzing the data. Respiratory rate will be measured at each timepoint specified in the protocol.

Baseline for these measures will be defined as the last pre-dose measurement in each study period.

The following endpoints will be determined:

- Change from baseline (CFB) in systolic and diastolic BP, pulse rate and respiratory rate
- The minimum and maximum post-dose systolic and diastolic BP, pulse rate and respiratory rate
- The maximum increase and decrease from baseline over all measurements taken postdose for systolic and diastolic BP, pulse rate and respiratory rate values

The maximum decrease and increase from baseline over all measurements taken post-dose will be calculated for supine systolic and diastolic blood pressures and pulse rates. The maximum increase from baseline will be calculated by selecting the maximum change from baseline over the respective period, except in the case where a participant does not show an increase. In such an instance, the minimum decrease should be taken. Similarly, the maximum decrease from baseline will be determined by selecting the minimum value of the change from baseline. In cases where a participant does not show a decrease, the minimum increase should be taken.

3.1.4. Electrocardiograms

A single 12-lead ECG will be obtained on all participants at screening, follow-up visit and at early termination (if applicable). 12-lead ECGs will be recorded in triplicate at all other times as detailed in the SoA in the protocol. The average of the triplicate readings collected at each assessment time will be calculated for each ECG parameter.

The average of the triplicate ECG measurements over the 3 pre-dose measurement times (-1H, -0.5H, and pre-dose 0H; total of 9 ECG measurements) collected before morning dose administration on Day 1 will serve as each participant's baseline value in each study period.

ECG endpoints include heart rate, QT interval, PR interval and QTcF and QRS complex. If not supplied QTcF will be derived using Fridericia's heart rate correction formula:

$$QTcF = QT / (RR)^{1/3}$$
 where $RR = 60/HR$ (if RR not provided).

The following endpoints will be determined:

- Change from baseline in QT, QTcF, PR, QRS interval and heart rate
- The maximum post-dose QTcF, heart rate, PR and QRS interval
- The maximum increase from baseline over all measurements taken post-dose for QTcF, heart rate, PR and QRS values

The maximum increase from baseline will be calculated by selecting the maximum change from baseline over the respective period, except in the case where a participant does not show an increase. In such an instance, the minimum decrease should be taken.

3.1.5. Continuous Cardiac Monitoring

Continuous cardiac monitoring will be performed using telemetry as outlined in the protocol.

All abnormal rhythms will be recorded and reviewed by the study physician for the presence of rhythms of potential clinical concern. The time, duration, and description of the clinically significant event will be recorded in the CRF.

Events deemed of clinical concern will be recorded as AEs and will be summarized as part of the standard AE outputs.

3.1.6. Neurological examinations

Neurological examinations may be conducted by a physician, trained physician's assistant, or nurse practitioner as acceptable according to local regulation at the nominal time points specified in the SoA. The neurological exam will consist of assessment of higher cortical function, the cranial nerves, motor function, deep tendon reflexes, sensory exam, and coordination and gait. Additional neurological examinations that are outside of SoA (eg, to evaluate an AE) may be conducted at the discretion of investigator. All neurological exams should be done to the extent needed to assess the participant for any potential changes in neurological status, as determined by the investigator (or designee). Changes in the timing or addition of timepoints for the neurological examinations may occur based on emerging data.

Any untoward neurological examination findings that are identified during the active collection period will be captured as AEs or SAEs, if those findings meet the definition of an AE or SAE, and will be summarized as part of the standard AE outputs.

3.1.7. Physical Examinations

Complete physical examinations will be conducted at screening or upon admission for a participant's first period in the study. At all other timepoints, a brief physical exam may be performed for the findings during a previous exam or new/open AEs at the investigators discretion. Height and weight will only be measured at the screening visit.

Physical examination findings collected during the study will be considered source record and will not be required to be reported, unless otherwise noted.

Any untoward physical examination findings that are identified during the active collection period will be captured as AEs or SAEs, if those findings meet the definition of an AE or SAE, and will be summarized as part of the standard AE outputs.

3.2. Secondary Endpoint(s)

Blood samples for PK analysis of PF-07853578 will be taken according to the SoA in the protocol.

The plasma PK parameters for PF-07853578, following oral dose administration, will be derived from the plasma concentration-time profiles using standard noncompartmental methods as detailed in Table 2, as data permit. Table 2 shows the analysis scale and method for each parameter.

In all cases, actual PK sampling times will be used in the derivation of PK parameters. If actual PK sampling times are not available, nominal PK sampling times will be used in the derivation of PK parameters.

The following plasma PK parameters as described in Table 2 will be determined:

Parameter	Analysis Scale	PF-07853578
AUC _{inf} *	ln	A, D
AUC _{last}	ln	A, D
C _{max}	ln	A, D
T _{max}	R	D
t _{1/2} *	R	D

Table 2. Summary of PF-07853578 plasma PK parameters to be calculated.

3.3. Other Endpoint(s)

3.3.1. Additional Plasma PF-07853578 PK Parameters

Additional plasma PF-07853578 PK parameters, as described in Table 3, will be determined:

Table 3. Additional PF-07853578 Plasma PK Parameters

Parameter	Analysis Scale	PF-07853578
AUC _{inf} (dn)*	ln	D
AUC _{last} (dn)	ln	D
$C_{max}(dn)$	ln	D
CL/F*	ln	D
V _z /F*	ln	D

^{*=}if data permits. Abbreviations: D=displayed with descriptive statistics as outlined in Table 5 in Section 6.3.1; dn = normalized to a 1 mg PF-07853578 dose; ln=natural-log transformed; R = raw (untransformed).

3.3.2. Plasma PF-07853578 PK Parameters During Food Effect Period (if conducted)

The plasma PF-07853578 PK parameters described in Table 2 and Table 3 will also be determined during the fed period.

3.3.3. Plasma PF-07853578 PK Parameters During IDS Oral Solution Period (if conducted)

The plasma PF-07853578 PK parameters described in Table 2 and Table 3 will also be determined after IDS oral solution administration.

3.4. Baseline Variables

Not applicable.

3.5. Safety Endpoints

See Section 3.1 for details.

^{*=}if data permits. Abbreviations: A=analyzed using a statistical model (if applicable); D=displayed with descriptive statistics as outlined in Table 4 in Section 6.2; ln=natural-log transformed; R = raw (untransformed).

4. ANALYSIS SETS (POPULATIONS FOR ANALYSIS)

Data for all participants will be assessed to determine if participants meet the criteria for inclusion in each analysis population prior to unblinding and releasing the database and classifications will be documented per standard operating procedures.

Participant Analysis Set	Description	Applicable Analysis (for additional information refer to Section 6)
Enrolled	"Enrolled" means a participant's, or their legally authorized representative's, agreement to participate in a clinical study following completion of the informed consent process and randomization to study intervention. A participant will be considered enrolled if the informed consent is not withdrawn prior to participating in any study activity after screening. Potential participants who are screened for the purpose of determining eligibility for the study, but do not participate in the study, are not considered enrolled, unless otherwise specified by the protocol.	
Evaluable	All participants assigned to study intervention and who take at least 1 dose of study intervention.	
Safety analysis set	All participants randomly assigned to study intervention and who take at least 1 dose of study intervention. Participants will be analyzed according to the study intervention they actually received.	Section 6.1 Safety Summaries and Analyses
PK Concentration Set	All participants randomly assigned to study intervention and who receive at least 1 dose of study intervention and in whom at least 1 plasma concentration value is reported.	Section 6.2, Section 6.3.1, Section 6.3.2, Section 6.3.3 PK Endpoints
PK Parameter Set	All participants randomly assigned to study intervention and who receive at least 1 dose of study intervention and have at least 1 of the PK parameters of interest calculated.	Section 6.2, Section 6.3.1, Section 6.3.2, Section 6.3.3 PK Endpoints

5. GENERAL METHODOLOGY AND CONVENTIONS

5.1. Hypotheses and Decision Rules

There is no statistical hypothesis testing planned for this study, and no statistical decision rules will be applied.

5.2. General Methods

Unless otherwise stated, all summaries and plots will be presented by dose and treatment as applicable. Each formulation of PF-07853578 administered during the study and fasting status will be considered as separate treatments.

Unless otherwise stated the summary tables and/or statistical analyses will only include a single pooled placebo group across all included cohorts. Placebo will be pooled from all dose escalation periods but not for the fed period (if conducted) and for IDS oral solution period (if conducted).

5.2.1. Analyses for Continuous Endpoints

Unless otherwise stated, continuous variables will be presented using summary statistics: number of observations, arithmetic mean, standard deviation, median, minimum and maximum values.

5.2.2. Analyses for Categorical Endpoints

Categorical variables will be presented using summary statistics: number of observations and percentages.

5.2.3. Mixed Effect Model

A mixed effects model with treatment as a fixed effect and participant as a random effect will be used for analysis of the:

- Effect of food on PF-07853578 PK
- PF-07853578 PK of IDS oral solution relative to the oral suspension formulation.

Estimates of the adjusted (least squares) mean differences (Test-reference) and corresponding 90% confidence intervals will be obtained from the model. The adjusted mean differences and 90% confidence intervals for the differences will be exponentiated to provide estimates of the ratio of adjusted geometric means (Test/Reference) and 90% confidence intervals for the ratios.

The mixed effects model will be implemented using SAS Proc Mixed, with REML estimation method and the Kenward-Roger degrees of freedom algorithm.

Residuals from the models will be examined for normality and the presence of outliers via visual inspection of plots of residuals vs predicted values and normal probability plots of residuals, but these will not be included in the clinical study report. If there are major

deviations from normality or outliers (where studentized [conditional] residuals are greater than 3 or less than -3), then the effect of these on the conclusions may be investigated through alternative transformations and/or analyses excluding outliers. Justification for any alternative to the planned analysis will be given in the report of the study if applicable.

Example code is shown in Appendix 1.

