5.3.1. Plasma Pharmacokinetic Parameters

Actual PK sampling times will be used in the derivation of plasma PK parameters.

If a PK parameter cannot be derived from a participant's concentration data, the parameter will be coded as NC (i.e., not calculated). (Note that NC values will not be generated beyond the day that a participant discontinues.)

In summary tables, statistics will be calculated by setting NC values to missing; and statistics will be presented for a particular treatment group/analyte with ≥3 evaluable measurements. For statistical analyses (i.e., mixed effects model), PK parameters coded as NC will also be set to missing; and analyses will not be performed for a particular parameter if more than 50% of the data are NC.

If an individual participant has a known biased estimate of a plasma PK parameter (due, for example, to an unexpected event such as vomiting before all the compound is adequately absorbed in the body), this will be footnoted in summary tables and may not be included in the calculation of summary statistics or statistical analyses.

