6.2. Secondary Endpoints

Plasma PK parameters for PF-07853578, as described in Section 3.2, will be listed and summarized descriptively for participants in the PK Parameter Set (as defined in Section 4). Missing values will be handled as detailed in Section 5.3. Each PK parameter will be summarized by dose (and formulation and fasting condition, if appropriate) as applicable.

Table 4. Summary Statistics for PF-07853578 Plasma PK Parameters

Parameter	Summary Statistics	
AUC _{last} , AUC _{inf} *, and C _{max}	N, arithmetic mean, median, cv%, standard deviation,	
	minimum, maximum, geometric mean and geometric	
	cv%.	
T _{max}	N, median, minimum, maximum.	

t _{1/2} .*	N, arithmetic mean, standard deviation, median,
	minimum, maximum.

^{*:} if data permit

Supporting data from the estimation of AUC_{inf} will be listed by dose and treatment (if applicable): terminal phase rate constant (kel); goodness of fit statistic from the log-linear regression (r²); the percent of AUC_{inf} based on extrapolation (AUC_{extrap%}); and the first, last, and number of time points used in the estimation of kel. This data may be included in the clinical study report.

The following plots will be presented using the PK Parameter Set (as defined in Section 4):

- Box and whisker plots for dose-normalized PK parameters [AUC_{inf} (dn), AUC_{last} (dn) and C_{max}(dn)] will be presented in logarithmic scale by dose and treatment (if applicable) and overlaid with observed values of individual participants and geometric means. Geometric means will have a different symbol than the individual values. Individual values from different cohorts will also have a different symbol. A footnote will be added to the plots to indicate that geometric means are presented and that data from all cohorts are presented on the plot.

The following will additionally be presented for the plasma concentration data using the PK Concentration Set (as defined in Section 4):

- a listing of all concentrations sorted by participant ID and nominal time post-dose for each dose and treatment (if applicable) separately. The concentration listing will also include the actual times. Deviations from the nominal time will be given in a separate listing.

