- a summary of concentrations by each nominal time post-dose (produced separately for each dose and treatment (if applicable)), where the set of statistics will include n, mean, median, standard deviation, coefficient of variation (cv), minimum, maximum and the number of concentrations above the lower limit of quantification.
- median concentration time plots (on both linear and semi-log scales) against nominal time post-dose by dose and treatment (if applicable). One plot for each scale will be presented, which will include all doses and treatments in the same plot.
- individual concentration time plots by dose (on both linear and semi-log scales) against actual time post-dose (there will be separate spaghetti plots for each dose and treatment (if applicable), with a line for each participant per scale).
- individual concentration time plots by participant (on both linear and semi-log scales) against actual time post-dose.

The nominal PK sampling time will be used for summary statistics and relevant median plots, whereas for individual participant plots by time, the actual PK sampling time will be used.

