6.3.2. Plasma PF-07853578 PK Parameters During Food Effect Period (if conducted)

Plasma PK parameters for PF-07853578 on Fed State as described in Section 3.3.2 will be listed and summarized descriptively as described in Section 6.2 for participants in the PK Parameter Set as defined in Section 4.

Natural loge transformed AUC_{inf} (as data permit), AUC_{last}, and C_{max} (dose-normalized prior to analysis, if appropriate) of PF-07853578 on fasted state or on fed state will be analyzed using a mixed effect model as described in Section 5.2.3, using only data from the respective periods that includes the two treatments of interest. The test treatment will be PF-07853578 administered with food in comparison to the reference treatment of PF-07853578 administered on fasted state.

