Appendix 1. PK Analyses – Example of SAS Code for mixed effects model

An example of the PROC MIXED code:

proc mixed data=tab.pk;
 class trt subject;
 model &var = trt / ddfm=KR;
 random subject /subject=subject;
 lsmeans trt/ diff cl alpha=0.1;
run;

Appendix 2. Categorical Classes for ECG and Vital Signs of Potential Clinical Concern Categories for QTcF

Absolute value of QTcF (msec)	>450 and ≤480	>480 and ≤500	>500
Increase from baseline in QTcF (msec)	>30 and ≤60	>60	

Categories for PR and QRS

PR (msec)	max. ≥300	
PR (msec) increase	Baseline >200 and	Baseline ≤200 and
	max. ≥25% increase	max. ≥50% increase
QRS (msec)	max. ≥140	
QRS (msec) increase from baseline	≥50% increase	

Categories for Vital Signs

Systolic BP (mm Hg)	min. <90	
Systolic BP (mm Hg) change from baseline	max. decrease ≥30	max. increase ≥30
Diastolic BP (mm Hg)	min. <50	
Diastolic BP (mm Hg) change from baseline	max. decrease ≥20	max. increase ≥20
Supine pulse rate (bpm)	min. <40	max. >120

Measurements that fulfill these criteria are to be listed in the report.

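### Does the ±3 residual limit in SAP 5.2.3 need to say which kind of studentized residual it means?

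*SAP*

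**What the plan says.** SAP 5.2.3 specifies a mixed model with treatment fixed and participant random, fitted by REML with Kenward-Roger degrees of freedom. It reports geometric mean ratios with 90% confidence intervals. Residuals are first inspected by eye, on residual-versus-predicted and normal probability plots that stay out of the study report. The same paragraph then gives the one numeric criterion, "outliers (where studentized [conditional] residuals are greater than 3 or less than -3". If it is met, or if normality clearly fails, "the effect of these on the conclusions may be investigated through alternative transformations and/or analyses excluding outliers", and any departure from the planned analysis must be justified in the report.

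The Appendix 1 code has the line "model &var = trt / ddfm=KR" and requests no residual or influence output, so it does not settle the residual type.

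Other relevant statements:

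- SAP 6.3.2 fits the food-effect model "using only data from the respective periods that includes the two treatments of interest"; SAP 6.3.3 restricts the IDS model in the same way.
- SAP 5.3.1 sets parameters that could not be calculated to missing and still fits the model, except that "analyses will not be performed for a particular parameter if more than 50% of the data are NC".
- SAP 6.2 plans box plots "overlaid with observed values of individual participants and geometric means" and "individual concentration time plots by participant (on both linear and semi-log scales) against actual time post-dose".
- SAP 5.1 states: "There is no statistical hypothesis testing planned for this study, and no statistical decision rules will be applied".

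**The concern.** With a data set this small, internal and external studentization are not interchangeable. An internally studentized residual is scaled by a variance that the suspect value has itself inflated, so it has a hard ceiling. If that ceiling is at or below 3, reporting that no residual exceeded 3 carries no information. An externally studentized residual has no such ceiling, but with few degrees of freedom values beyond 3 are not rare in sound data.

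The stake is the food-effect or formulation ratio. One aberrant profile among six can move it noticeably, and the only numeric criterion that could prompt an analysis without that profile depends on a choice the SAP leaves open.

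**Working it through.** The documents give no detection rate for this rule, so there is no stated figure to reproduce.

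**Inputs.** Protocol 4.2 and 9.5 plan 6 participants on active drug per period. Two periods enter each model, so N = 6 + 6 = 12. Two treatments give p = 2 fixed-effect parameters. The documents state no CV, so every CV below is an assumption, written between/within participant.

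**Ceiling for internal residuals.** The conditional residual is proportional to Py, where P is the REML projection matrix. Its internally studentized form is r = (Py)ᵢ / √Pᵢᵢ. At the REML solution y′Py = N − p. Cauchy-Schwarz gives (Py)ᵢ² ≤ Pᵢᵢ · y′Py, so |r| ≤ √(N − p):

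- N = 12: √10 = 3.16
- N = 11: √9 = 3.00, which is not beyond 3
- N = 10: √8 = 2.83

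No CV is needed for this. In simulation at N = 11 the largest residual stayed below 3.000, even with one value at a thousandth of its expected level.

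**Conversion between the two types.** At a fixed variance ratio, t = r·√[(N − p − 1)/(N − p − r²)]. For N = 12:

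- Internal 3: t = 3·√(9/1) = 9.
- External 3: 9(10 − r²) = 9r², so r² = 5 and r = 2.24.

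**What the internal limit detects at N = 12.** Data are simulated log-normal, with one value at a tenth of its expected exposure.

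| Between/within CV | Flagged, six complete pairs |
|---|---|
| 10/10% | 99% |
| 20/10% | 69% |
| 20/20% | 35% |
| 30/20% | 16% |
| 40/30% | 3% |

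With six complete pairs, detection falls to one half at a total CV of 24.6–27.8%, depending on how variance splits between and within participants. For a threefold-low value the crossing is near 12% (57.4% flagged at total CV 11.3%, 42.4% at 12.8%).

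These figures depend on pairing. Randomization is 6:2 in each period with up to two placebo doses per participant, and the PK Parameter Set does not require both treatments. Four, five or six pairs are therefore possible. If the two placebo participants were drawn independently in each period (an assumption), the probabilities would be 15/28 = 54%, 12/28 = 43% and 1/28 = 4%. With four or five pairs, a tenfold-low value in an unpaired participant is flagged in at most 0.1% of runs at every CV tried, because REML assigns it to between-participant variance.

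**What the external limit does at N = 12.** With six pairs it flags 59–100% of tenfold-low profiles across CV 10/10 to 60/50. It also flags 7–16% of clean data sets, or 29–35% if the variances are re-estimated after each deletion. With four or five pairs and an unpaired low value, detection is 57–75% at CV 40/30 and 29–38% at 60/50.

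**Effect of one such profile.** With six pairs the ratio is multiplied by f^(1/6): (1/3)^(1/6) = 0.83 and (1/10)^(1/6) = 0.68.

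**What a leave-one-participant-out listing would add.** At CV 40/30 the median highest-to-lowest ratio (5th–95th percentile) is 1.23 (1.11–1.40) in clean data, 1.37 (1.19–1.62) with a threefold-low profile and 1.75 (1.48–2.06) with a tenfold-low one. It separates only the tenfold case, which six plotted individual values would usually show as well.

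**The case for a change.** The case for changing the SAP is that internal 3 and external 3 are far apart at this size, that the model is still run when values are missing, and that AUCinf, analysed only where data permit, could easily drop to 11 values. The residual plots are kept out of the report, so a reader could not check a statement that nothing exceeded 3. An analysis excluding outliers should not hinge on an unstated choice, and naming the type costs one sentence.

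The silence and the algebra both stand. The practical consequence is much weaker:

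- The first check in SAP 5.2.3 is visual and does not depend on the ±3 limit.
- SAP 5.3 and 5.3.1 already allow exclusion for vomiting, non-compliance, anomalous concentrations or a known biased estimate, without any residual trigger. Protocol 6.5 has site staff confirm ingestion.
- Parameters are listed, and individual values and profiles are plotted. The reader can see an aberrant profile without the residual plots.
- A flag permits an investigation and requires nothing. An alternative analysis must be justified in the report.

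N is not fixed at 12 either. The counts are approximate, Protocol 4.1 allows replacements and Protocol 6.6 allows cohort expansion. Eight pairs would raise the internal ceiling to √14 = 3.74.

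**Conclusion.** The gap is real, but it is missing detail that the analyst fills when fitting the model. SAP 5.2.3 does not name the residual type. Read as internal, the ±3 limit cannot be passed with 11 or fewer values and is weak at 12 unless variability is low and the low value belongs to a participant with both treatments. Read as external, it flags an appreciable share of clean data sets. Neither reading gives a criterion that could carry a decision, so stating the type would bring no real gain. A leave-one-out listing would be an addition of preference, not a repair, and would leave the all-data ratio unchanged.

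The ceilings and the conversion are exact, the conversion at a fixed variance ratio. Detection and false-flag rates rest on assumed CVs and on the pairing layout. Figure 1 is not shown, so a planned sequence that gives complete pairs cannot be ruled out. The limit touches only two optional exploratory comparisons, with no hypothesis test or decision rule attached. No primary or secondary conclusion depends on it, and no change to the plan is needed.
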